9.4.2 Analysis of the Secondary Endpoint(s)

Two secondary endpoints to be measured are length of time until additional analgesia needed after initial treatment (GNB or conventional analgesia) and ED LOS. Both of these endpoints are interval/ratio variables measured in hours. Additional analgesia time will be assessed at 24-36 hours after intervention by phone call or EMR if still in the ED or admitted to the hospital. ED-LOS will be assessed by EMR chart review. To assess differences between treatment arms for both these time endpoints, either a 2-sample t-test (normally distributed) or a Wilcoxon rank-sum test (positively skewed) will be performed.

The final secondary endpoint is the 6 questions on the modified APS-POQ-RED administered. Each of 5 questions are on an ordinal scale from 0-10. For each question, a 2-sample t-test will be performed.

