The control arm will be treated with oral, intravenous, or topical analgesics, as per the treating clinician's discretion. Patients will be observed on continuous cardiorespiratory monitoring in the ED for at least 30-minutes following treatment to evaluate for treatment effect and adverse events. Patients will be discharged from the ED when their pain is sufficiently controlled, and they are agreeable for discharge. Of note, patients in both treatment arms will be eligible for additional analgesics, as needed, at any point after enrollment. This will be recorded and evaluated during analysis. At either 1-hour after enrollment or at the time of discharge from the ED (whichever occurs first), patients of both treatment arms will be again asked to rate their pain severity on the NRS and asked to complete the modified APS-POQ-RED. This survey will be conducted either by RAs (during daytime hours, if available) or the performing physician (if overnight). Patients will subsequently receive a phone call approximately 24 to 36 hours after the treatment by a member of the study team (performing physician, RA, or the clinical research coordinator (CRC) from the Emergency Ultrasound Division) to evaluate the duration of analgesia. If the block is performed during overnight hours, the follow-up call will take place the next day (between 24 to 36 hours after treatment). After this assessment, the participant's involvement in the study will be concluded. Only in cases where an adverse event occurred that either requires hospitalization or ambulatory follow-up will a participant's participation last longer than 24 hours. All data collected by the RA, the CRC, or the performing physician will be stored in REDCap. The RAs will transmit all research data, including an encrypted medical record number (MRN) and all pain scale responses obtained from the study participants to the Ultrasound Division's CRC, who will be responsible for storing and managing data on REDCap.

Patients with large knee effusions will not be included in the study as large effusions can make the GNB more difficult to perform by distorting the anatomical and sonographic landmarks, and we wish to avoid the additional risk of inadvertent intra-articular injections. In our experience, we have been able to perform the GNB on patients with small and moderate sized effusions without difficulty.

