9 STATISTICAL CONSIDERATIONS

9.1 Statistical Hypotheses

Primary endpoints:

- H_0 : Mean change in pain levels pre / post GNB = Mean change in pain levels pre / post conventional therapy
- H_1 : Mean change in pain levels pre / post GNB \neq Mean change in pain levels pre / post conventional therapy

Secondary endpoints:

- H_0 : Mean duration of analgesia for patients receiving GNB = Mean duration of analgesia for patients receiving conventional therapy
- H_1 : Mean duration of analgesia for patients receiving GNB \neq Mean duration of analgesia for patients receiving conventional therapy
- H_0 : Mean APS-POQ-RED score for patients receiving GNB = Mean APS-POQ-RED score for patients receiving conventional therapy
- H_1 : Mean APS-POQ-RED score for patients receiving GNB \neq Mean APS-POQ-RED score for patients receiving conventional therapy
- H_0 : Mean ED LOS for patients receiving GNB = Mean patient satisfaction for patients receiving conventional therapy
- H_1 : Mean ED LOS for patients receiving GNB \neq Mean patient satisfaction for patients receiving conventional therapy

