9.4 Statistical Analyses

9.4.1 General Approach

Prior to analysis, all primary and secondary outcome measures will be summarized with descriptive statistics (mean \pm standard deviation (SD) or median and IQR), their distributions examined, tested for normality and transformed using log base 10 as needed. Additionally, all

demographics will be summarized using mean \pm SD or median and IQR, for continuous variables and frequencies and percentages for categorical variables. Results from statistical testing for continuous variables, will be presented with p-values and 95% confidence intervals for tests using means or medians and IQR if a non-parametric test is used. For categorical variables, the chi-square or Fisher's exact test will be performed to examine whether treatment arms differ with regard to demographics and other baseline variables. Similarly, for side effects, descriptive statistics and Fisher's exact tests will be performed for possible differences between the treatment arms. Regardless of type statistical test, all will be two-sided.

The primary efficacy endpoint is change in pain level as measured on the NRS at baseline (pre intervention) and at post intervention (either 1-hour post-enrollment or at time of ED discharge, whichever occurs first) in both treatment arms. The NRS is an ordinal variable, measured on a 0-10 scale and will be treated as a repeated measure. To determine differences in pain level between GNB and conventional analgesia treatment arms, a 2-factor analysis of variance in repeated measures will be performed where treatment arm is the grouping factor and time (pre/post) is the repeated measure. To adjust for multiple comparisons, post-hoc pairwise Tukey-Kramer tests will be performed. Results will be presented as means \pm 95% confidence intervals for each treatment arm/time point. Shapiro-Wilkes test will be used to test for normality. If not normally distributed, data will be transformed using log base 10 transformation. If missing time points, analysis type will change to a mixed general linear model where treatment arm is a fixed factor and time is random.

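### Duration of analgesia is tested as a mean of fully observed hours, but patients still event-free at the 24-36 h contact supply only a lower bound, so that mean cannot be estimated

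*Protocol*

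**What the plan says.** Section 9.4.2 defines the endpoint as "length of time until additional analgesia needed after initial treatment" and groups it with ED length of stay: "Both of these endpoints are interval/ratio variables measured in hours". For both, "either a 2-sample t-test (normally distributed) or a Wilcoxon rank-sum test (positively skewed) will be performed". Section 9.1 states the null hypothesis as "Mean duration of analgesia for patients receiving GNB = Mean duration of analgesia for patients receiving conventional therapy". Section 9.4.1 adds a log10 transformation where needed and reports "medians and IQR if a non-parametric test is used".

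On follow-up, 9.4.2 says "Additional analgesia time will be assessed at 24-36 hours after intervention by phone call", or from the EMR if the patient is still in the ED or admitted. Section 4.1 says "Patients will subsequently receive a phone call approximately 24 to 36 hours after the treatment", and after that assessment the participant's "involvement in the study will be concluded". Section 6.4 has medications given after treatment recorded in the EMR and REDCap. Section 7.3 covers patients who cannot be reached. No section says what value a patient receives who is reached and has needed no further analgesia.

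**The concern.** The endpoint is an event time with a short, fixed end of observation. For a patient without the event at contact, the data say only that the time exceeds the contact time. A mean over all patients needs the part of the distribution beyond contact, and nothing is collected there. The choice between t-test and rank-sum turns on normality or skewness, not on whether the times were observed.

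The protocol makes such patients plausible. Section 2.2.1 gives a duration of 2 to 9 h, extending to 24 h with adjuvants, and the block contains an adjuvant. Section 2.3.2 reports relief beyond 24 h in the investigators' own experience, and 4.1 hypothesises longer analgesia with GNB. It is not certain, because those sections describe drug action and pain relief rather than requests for analgesia, and 7.1 foresees further analgesics 60 minutes after a block.

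At stake is the effect estimate for the first-listed secondary objective: the reported hours gained would not be the mean duration named in 9.1.

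**Working it through.** **Inputs.** From the protocol: 17 per arm (9.2, sized for the primary NRS endpoint) and contact at 24-36 h (4.1, 9.4.2). The protocol gives no design figure for this endpoint, so there is none to reproduce. Assumed: contact uniform over 24-36 h, and durations with S(t) = exp{-ln 2 (t/m)^k}, where m is the median and k = 1 (exponential) or k = 2 (Weibull).

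**1. What is observed.** With T the event time and C the contact time, the data are min(T, C) and whether T ≤ C. The mean in 9.1 is the integral of S(t) from 0 to infinity, but the data inform S(t) only to 36 h at most. A log10 transformation turns T > C into log T > log C, which is still only a bound.

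**2. Event-free share at contact.** p = (1/12) × integral of S(u) from 24 to 36. For the exponential, with λ = ln 2/m, p = (e^(-24λ) - e^(-36λ))/(12λ).

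- m = 9 h: λ = 0.0770; (0.1575 - 0.0625)/0.924 = 10.3%.
- m = 24 h: λ = 0.0289; (0.5000 - 0.3536)/0.347 = 42.3%.

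| GNB median | Exponential | Weibull, shape 2 |
|---|---|---|
| 9 h | 10.3% | 0.1% |
| 12 h | 18.0% | 1.9% |
| 24 h | 42.3% | 34.4% |
| 36 h | 56.2% | 61.8% |

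**3. Mean difference if call time is entered as the value.** If everyone is called at time t, an arm's mean is R(t), the integral of S from 0 to t; for the exponential this is (1 - e^(-λt))/λ. For exponential medians of 24 h (GNB) and 8 h (control):

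- t = 24 h: 17.31 - 10.10 = 7.2 h.
- t = 36 h: 22.38 - 11.03 = 11.4 h (11.35 before rounding).
- True means: 34.62 - 11.54 = 23.1 h.

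The Weibull figures are 10.9, 15.1 and 17.0 h. These are the ends of the window. Calls spread over 24-30 h against 30-36 h give 8.3 against 10.4 h (exponential) and 12.3 against 14.3 h (Weibull), a shift of about 2 h. The sampling SD of the difference at 17 per arm is about 3.5 h and 2.3 h. At Weibull medians of 12 and 8 h the dependence almost vanishes: 4.0 h with all calls at 24 h and 4.3 h at 36 h, against a true 4.3 h.

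**4. Dependence on coding.** For exponential medians of 24 and 6 h (true difference 26.0 h), entering call times gives 11.6 h and dropping event-free patients gives 5.3 h. The difference restricted to 24 h is 9.2 h.

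**5. Rank-sum branch.** If all event-free patients share the top rank, the GNB sample median is an observed event whenever at least 9 of 17 have the event. By simulation that is over 99% of trials at a 12 h median, 75-91% at 24 h and 16-29% at 36 h. Entering differing call times instead puts an arbitrary order on these patients.

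**6. Error rate and power.** With equal arms and the same call timing, simulated rejection is 4.3-5.8%. At exponential medians of 24 and 8 h, power is 78% for log-rank, 74% for the t-test on call times and 70% for rank-sum (69% tied at 24 h). Part of log-rank's lead is its advantage under proportional hazards. If one arm were called at 24-30 h and the other at 30-36 h, equal durations with medians of 24-48 h would be rejected in 11-23% of trials (t-test) or 19-64% (rank-sum); the rank-sum test on times capped at 24 h holds 4-5%.

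**7. The 24 h horizon.** For exponential medians of 24 and 8 h the restricted difference is 7.21 h. Its Kaplan-Meier estimate averages 7.21 h (95% CI coverage 94%). It averages 7.17 h (94%) if calls start at 22 h, and 7.23 h (93%) if 10% are unreached and censored at an assumed 1-4 h, unrelated to duration. A test on it has 72% power.

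**The case against.** The strongest reply is that the problem is conditional. If durations follow the 2-9 h range in 2.2.1, very few patients are event-free at contact and the planned mean is nearly right. That stands: no figure in the protocol settles the share.

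Second, the t-test applies only to normal data. In the exponential scenarios, with call times entered, a Shapiro-Wilk test rejects in at least one arm in roughly three quarters or more of trials, so the plan would mostly move to a transformation or to rank-sum. This also stands, but with Weibull times rejection is only 18-55%, so the t-test branch remains live, and the hypothesis in 9.1 concerns the mean whichever test is used.

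Third, a value for event-free patients is a coding rule that an SAP could supply. A rule could be added there, but the unrestricted mean in 9.1 would remain beyond the data. The SAP would have to change the stated target.

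Fourth, the EMR route means that in-hospital events do not depend on the call. True, but it does not extend follow-up for a discharged patient.

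A reader might also infer that 4.4 and 7.3 contradict each other on unreached patients. They are not shown to: 4.4 describes patients who also refuse the questionnaire, and 7.3 keeps whatever was already obtained. Nor is a log-rank test required, since time capped at 24 h is fully observed for everyone reached at or after 24 h.

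**Conclusion.** The point holds for one secondary endpoint. The mean named in 9.1 cannot be estimated from follow-up that stops at 24-36 h when any patient is still event-free, and log10 does not help. The rank-sum branch is affected less, and works if event-free patients share one top rank.

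The size rests on the assumed distributions, from negligible at short durations to about a 2 h shift between early and late calls at medians of 24 and 8 h. A reader might infer a false-positive risk or a serious loss of power. The documents do not support either: error stays near nominal while call timing is alike in both arms, no section suggests that it differs, and the power differences are modest. The harm is an effect estimate that is undefined as stated. ED length of stay is not affected.

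**What to change.** In 9.4.2, for this endpoint only, define the outcome as time to additional analgesia restricted to a common 24 h horizon, with event-free patients set to 24 h. Reword the duration hypothesis in 9.1 to the mean restricted to 24 h. Report the difference in that mean with a 95% CI, and let the rank-sum test treat event-free patients as tied at 24 h. For patients contacted before 24 h or not reached, censor at the last time their status is known, including from the EMR, and estimate the 24 h restricted mean by Kaplan-Meier. A log-rank test is optional. Record in REDCap whether the event occurred and the last time at which status is known.

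The cost is one or two sentences in 9.4.2, one in 9.1 and two REDCap fields, with no new calls or visits. The downside is that nothing is estimated beyond 24 h. No gain in power is claimed. The change is best made before the interim look at secondary endpoints planned in 9.4.5 after 30 patients.

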3 STUDY OBJECTIVES AND ENDPOINTS

OBJECTIVES	ENDPOINTS	JUSTIFICATION FOR ENDPOINTS
Primary		
Pain Reduction To determine whether patients receiving a GNB for knee pain experience greater pain reduction compared to conventional analgesia	Difference in pain level as measured by NRS at pre-intervention (GNB or conventional) and at either 1-hour after enrollment or at time of ED discharge, whichever occurs first (post intervention)	This endpoint will evaluate whether the GNB provides a clinically meaningful reduction in pain compared to conventional analgesia.
Secondary		
Duration of Analgesia To determine whether patients who receive a GNB experience a longer duration of analgesia compared to those who receive conventional analgesia	Difference in duration of analgesia, assessed by a follow-up telephone call at 24-36 hours post intervention	This endpoint will evaluate whether the GNB will result in longer duration of analgesia compared to conventional analgesia.
Patient Reported Outcomes, including Patient Satisfaction To determine whether patients who receive a GNB report higher patient satisfaction compared to those who receive conventional analgesia	Difference in functionality/satisfaction as measured by the APS-POQ -RED between GNB and conventional analgesia. Questionnaire administered at either 1-hour post enrollment or at time of ED discharge, whichever occurs first.	This endpoint will evaluate whether patients will have improved satisfaction with treatment when receiving the GNB as compared to conventional analgesia using a modified version of the APS-POQ designed for the ED
Reduce ED LOS To determine whether patients who receive a GNB have shorter ED length of stay (LOS) compared to those who receive conventional analgesia	Difference in ED LOS between GNB and conventional analgesia, as determined by time from enrollment in study to time of ED discharge.	This endpoint will evaluate whether treatment with the GNB can shorten ED LOS compared to conventional analgesia

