12 APPENDIX

12.1 Schedule of Activities (SoA)

12.2 The American Pain Societies – Patient Outcome Questionnaire Revised for the Emergency Department (APS-POQ-RED)

The following question is about the pain you experienced during your stay in the emergency department:

- On this scale, please tick the current pain you have after treatment in the emergency department (from “0” = no pain to “10” = worst possible pain).

Tick the one number below that describes how your current pain interferes with or prevents you from different activities (from “0” = no did not interfere to “10” = completely interfered).

- During activities in bed such as turning, sitting up, repositioning:
- During activities out of bed such as walking, sitting in a chair, standing:

On this scale, please tick the number describes how your current pain causes you to feel different emotions (from “0” = not at all to “10” = extremely)

- Anxious
- Frightened
- Helpless

In the emergency department, how much pain relief did you receive?

- Please tick the percentage that best shows how much relief you have received for all your pain treatments combined.

This question asks about your overall satisfaction with your pain control.

- Tick the number that best shows how satisfied with the results of your pain treatment in the emergency department (from “0” = extremely dissatisfied to “10” = extremely satisfied)

Modified from:

END OF DOCUMENT

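### Sections 9.1 and 9.4.2 give conflicting analyses of the APS-POQ-RED, and no test is designated for the satisfaction objective

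*Protocol*

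**What the plan says.** The secondary objective in Protocol section 3 is: "To determine whether patients who receive a GNB report higher patient satisfaction compared to those who receive conventional analgesia". The endpoint beside it is wider. It covers both functionality and satisfaction, as measured by the APS-POQ-RED.

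Section 9.1 gives this endpoint one null hypothesis: "Mean APS-POQ-RED score for patients receiving GNB = Mean APS-POQ-RED score for patients receiving conventional therapy". The alternative has the same form. No section says how such a score is built.

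Section 9.4.2 forms no score. It says "The final secondary endpoint is the 6 questions on the modified APS-POQ-RED administered", then "Each of 5 questions are on an ordinal scale from 0-10", then "For each question, a 2-sample t-test will be performed". The questions are not listed there, and no adjustment across them is stated. The Tukey-Kramer procedure in 9.4.1 belongs to the primary pain analysis.

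Appendix 12.2 prints the instrument. It includes a relief item, "Please tick the percentage that best shows how much relief you have received", and one satisfaction item, "Tick the number that best shows how satisfied with the results of your pain treatment in the emergency department", scored 0-10.

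For ED length of stay, the null hypothesis in 9.1 reads: "Mean ED LOS for patients receiving GNB = Mean patient satisfaction for patients receiving conventional therapy". The alternative carries the same mismatch.

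**The concern.** The same endpoint has two stated analyses: one test of a single score in 9.1, and one test per question in 9.4.2. The set of questions in 9.4.2 does not match the printed questionnaire on a plain count, so a reader cannot be sure which items are tested or how the emotion items enter. Neither section says which result answers the satisfaction objective.

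What is at stake is the secondary claim about satisfaction. The trial is open-label and the items are subjective. With no designated test, that claim could be supported after the fact by relief, by interference, by an emotion item, by the satisfaction item, or by some average of them. Section 9.4.5 also plans an interim look at the secondary endpoints after 30 patients, so the choice could be made with data in view.

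The length-of-stay hypotheses are a separate, smaller matter. As written they set hours in one arm against satisfaction in the other.

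**Working it through.** **Step 1. Count the items in Appendix 12.2.**

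- Current pain: 1 item, 0-10, high is worse.
- Interference, in bed and out of bed: 2 items, 0-10, high is worse.
- Emotions (anxious, frightened, helpless): 3 items, 0-10, high is worse.
- Relief: 1 item, percentage, high is better.
- Satisfaction: 1 item, 0-10, high is better.

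Total: 1 + 2 + 3 + 1 + 1 = 8 answer items. On 0-10: 1 + 2 + 3 + 1 = 7. High is worse on 6 and better on 2.

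**Step 2. Try to reproduce the counts in 9.4.2 (6 questions, 5 on 0-10).**

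- Every answer item counted: 8 and 7. No match.
- Every question stem counted once: 5 and 4. No match.
- Interference as one question, emotions as three: 1 + 1 + 3 + 1 + 1 = 7, with 6 on 0-10. No match.
- Interference as two questions, emotions as one: 1 + 2 + 1 + 1 + 1 = 6, with 5 on 0-10. Match.

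Among groupings that keep every printed item, only the last works. It treats the two multi-part stems differently, and it leaves open whether the emotion block gets three tests, one test on an average, or something else. Leaving out two of the 0-10 items would also give 6 and 5, but no section says that any printed item is left out.

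**Step 3. Set 9.1 against 9.4.2.** Section 9.1 needs one number per patient. Section 9.4.2 yields six or eight separate comparisons. No scoring or reverse-coding rule connects them.

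**Step 4. Size of the multiplicity.** For k independent tests at two-sided 0.05 with no true difference, the chance of at least one false positive is 1 - 0.95^k.

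- k = 1 (satisfaction item alone): 5%.
- k = 6: 1 - 0.95^6 = 0.265, about 26%.
- k = 8: 1 - 0.95^8 = 0.337, about 34%.

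The items come from one patient at one time and are likely to be positively correlated, so the true figure lies between 5% and these values.

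**Step 5. Why an undefined score matters (illustration only).** Suppose the block improves every 0-10 item by 1 point and relief by 10 percentage points. An unreversed mean of the eight items moves by (-6 + 1 + 1)/8 = -0.50 if relief is rescaled to 0-10, and by (-6 + 1 + 10)/8 = +0.63 if relief stays on 0-100. The same benefit changes sign with a scoring choice that the protocol does not state. The protocol does not plan either calculation.

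**Step 6. Length of stay.** Section 3 defines the endpoint as the difference in ED length of stay between arms, and 9.4.2 compares it in hours between arms by t-test or Wilcoxon. Only the hypotheses in 9.1 bring in satisfaction.

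**The case against.** The strongest defence is that 9.4.2 is the operative section and already contains a usable test. The questionnaire has one 0-10 satisfaction item, and a between-arm t-test on it answers the objective. Under the only grouping of all printed items that matches the stated counts, that item is among the six. This stands. A reader might infer that no valid test exists, but the documents do not support that: a valid test is probably planned and is simply not designated.

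A reader might also infer that the trial will analyse a composite whose sign can flip. No section defines a composite, and the mean score in 9.1 could be loose wording for the arm mean of each question. The figures in step 5 therefore show only why a score needs a rule.

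It would be wrong to read 34% as the risk of a false satisfaction claim. It is the chance of a false positive on any of eight independent items.

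The item counts can be reconciled, so they do not show that a different instrument was intended. The current-pain item overlaps with the primary outcome, but it is part of the questionnaire and is not an error. Functionality is part of the endpoint in section 3, so the interference items cannot simply be dropped.

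Finally, the length-of-stay wording does not invalidate that analysis, because section 3 and 9.4.2 have it right.

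It can be added that item scoring and secondary multiplicity are often left to a statistical analysis plan, which is not at hand. That would excuse silence. It does not excuse two sections of the protocol stating different analyses of one endpoint.

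**Conclusion.** The point holds as a contradiction within the protocol. Section 9.1 tests one undefined score, 9.4.2 tests each of six questions without adjustment, and Appendix 12.2 prints eight items that run in opposite directions. The set of tests is not determined, and no test is designated for the satisfaction objective.

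The size is moderate. If any item result could be used, the chance of at least one false positive is at most 26% for six tests or 34% for eight. These bounds assume independence or positive correlation and no true difference on any item. A single designated satisfaction test carries 5%. The length-of-stay hypotheses are a copying slip with no effect on the planned analysis, but the formal hypotheses are wrong as written.

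The primary endpoint is untouched. The correction is worth making before the interim look at 30 patients.

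**What to change.** - In 9.1, replace the mean-score hypothesis with a two-sided between-arm comparison of the 0-10 satisfaction item, designated as the single test of the satisfaction objective.
- In 9.4.2, list the eight items (seven on 0-10, one percentage) and give the direction of each. Correct the counts.
- Keep the two interference items, which carry functionality, and the five remaining items as supportive. Report each with a between-arm estimate and 95% confidence interval.
- In 9.1, restate both length-of-stay hypotheses as mean length of stay with the block against mean length of stay with conventional therapy.

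This changes wording only, with no new data and no change to procedures. The cost is that the other seven items, including functionality, lose confirmatory standing. If the investigators want functionality to keep it, they would have to name its item or items as a further designated test and say how the error rate is shared.
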